6.1.2 ADMINISTRATION AND/OR DOSING

Both interventions consist of 10 1-1.5 hour sessions over 12 weeks delivered in an individual, face-to-face format in participants' homes and/or communities by trained licensed occupational therapists (OTs). Care partners are also invited to participate.

A complete intervention is defined as completion of 10 OT sessions.

6.2 FIDELITY

6.2.1 INTERVENTIONIST TRAINING AND TRACKING

Training: MC training will consist of a 2-day PI and Co-I led workshop and regular meetings. Control training will consist of a 1-day PI led workshop and regular meetings. Both will involve reading, didactic instruction, interactive discussions and activities, role-playing, and videotaped examples. Each therapist will observe the PI conduct treatment with 1 participant and then will conduct treatment with 1-2 participants under PI supervision. The Co-I has extensive experience training and supervising OTs in the MC Approach^{49,74,75}, and the PI has extensive experience administering it. The study OTs will have requisite knowledge in metacognitive strategy training and task-oriented training and clinical experience with PD.

Supervision: We will audiotape all treatment sessions, and the PI and Co-I will review the tapes and meet with the therapists to reinforce training, correct problems, and discuss issues. Initially, 50% of the tapes

will be reviewed, and the teams will have weekly meetings; this will reduce to 20% review and fewer meetings when appropriate⁵⁶.

Assessment: Interventionist fidelity is a primary outcome of this study (Aim 2a) and thus will be formally assessed. *See section 8.1.*

6.3 MEASURES TO MINIMIZE BIAS: RANDOMIZATION AND BLINDING

Participants will be randomized to treatment arm (MC, Control)* stratified by sex and MoCA score [25/26]⁶⁵. The study statistician created a randomization process that is implemented through REDCap by an independent person ([name]). Immediately after a participant completes Pre assessment, the tester informs [name], via email, of their study ID, sex, and MoCA score (stratification variables). Within 2 days of being informed, [name] will use the REDCap randomizer to assign treatment group and will inform the corresponding therapists, via email, that a participant has been assigned to their group. Only [name] and the statistician can view the randomizer and its results. To maintain PI blinding during therapist supervision, the participants or treatment sessions under discussion will not be identified by study ID.

Personnel collecting Pre, Post and Follow-up data, which includes the study coordinator, will remain blind to treatment arm throughout the entirety of the study. They will not know which therapists are administering which intervention. Inadvertent unblinding of testers will be documented (yes/no, notes). Most of the outcomes, including the primary efficacy outcome (BGSI, Aim 3), are collected via computer, so inadvertent unblinding should not bias the data.

Personnel responsible for rating the audio files for fidelity (Aim 2) will be blind to study purpose. Due to the nature of their work, they will likely come to understand that there are two general intervention approaches being delivered and which therapists are delivering which approach; however, having no knowledge of the study aims and hypotheses and clear criteria for rating should reduce any associated biases in their ratings.

Participants will be aware that they have been randomly assigned to one of two interventions, but they will be given no information on what the other intervention entails, nor will they be informed which is the hypothesized “active” (MC) or Control intervention. In the Follow-up assessment, participants will be asked if they think they received the active or control intervention (yes/no/I don’t know with an option to provide an open-ended response describing why).

*Randomization ratios over the course of the study due to therapist availability:

- November 2019-December 2020 = 2:1, MC:Control
- January 2021- ~2021 = 1:2, MC:Control
- ~July 2021- = 1:1, MC:Control

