9.2 SAMPLE SIZE DETERMINATION

We will enroll 30 participants per group ($N = 60$). Although not required for an R21 proposal, we provide power analyses for our feasibility and fidelity hypotheses (Aims 1 & 2) assuming 15% attrition (see Table). We also estimate power for our (exploratory) pre-post comparisons of treatment effect (Aim 3). Based on our preliminary data (Goal Attainment $\Delta M = 2.4$, $SD = 0.97$), with $n = 30$ per group we will be able to detect mean differences in change of 0.85 in Attainment (2-tailed, $\alpha = 0.05$, 90% power). However, we want to reiterate that our reason for measuring treatment effect in this study is not to demonstrate efficacy but to obtain effect size estimates to power an efficacy trial. Our proposed sample size will provide enough information to achieve our aims and is feasible to accomplish in the timeframe of an R21.

Confidence bounds around target thresholds assuming 15% attrition (for Aim 2) and 95% confidence level.		
Aim	Outcome (with preliminary data source reference)	Target (Lower, upper)
1	Recruitment and retention	85% (73 – 93)
2a	Adherence (n=153 observations) ⁶¹	80% (78 - 82)

2a	Proficiency (n=153 observations) ⁶¹	3 (2.9 – 3.1)
2b	Acceptance: CSQ ⁵³	24 (23.8 – 24.2)
2b	Receipt: PRPS ⁷⁸	4 (3.8 – 4.2)
2b	Enactment: Homework completion ⁵³	80% (75 – 85)

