For the Aim 2 outcomes, we will calculate mean scores $\pm 95\%$ confidence bounds (CBs) and compare them to our stated thresholds. To assess treatment differentiation, we will compare Proficiency scores for the MC and Control sessions using *t*-tests. We can also categorize participants using cutoffs (e.g., homework: <50% = Poor, 50-79% = Fair, $\geq 80\%$ = Good) for descriptive purposes and compare the MC and Control groups’ scores on outcomes using appropriate non-parametric tests.

Aim 3: Obtain preliminary estimates of the MC approach's effect on patient-reported functional cognition.

- H3 (exploratory): MC participants will report greater improvement in functional cognition than Control participants immediately and 3 months after treatment.

We will compare treatment effects (Goal Attainment) using mixed model repeated measures ANOVA (2: group X 3: time point). We chose this model because we want to use statistical contrasts to compare pre-post and pre-follow up changes across group. We will evaluate the pattern of correlations within subjects and test various correlation structures as appropriate using Akaike's information criteria and the Schwarz Bayesian criteria. However, our purpose is not to demonstrate efficacy, but rather to obtain effect size data to inform sample size calculations for a definitive RCT. To this end, we will generate mean change between the time points with 95% CIs. We will compare these data to the suggested minimally clinically important difference (≥ 2 points improvement)⁸⁹ to help determine the appropriate sample size to test the hypothesis that, in addition to being superior to the Control treatment, MC produces a clinically significant effect⁹⁰. We will also create a sample size table for various effect size values due to uncertainty of pilot estimates⁹¹.

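### Allocation runs 2:1, then 1:2, then 1:1 over calendar time, but the Aim 3 model has no period-by-time term, so any period effect on change in Goal Attainment would bias the MC-Control contrast

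*Combined protocol and SAP*

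**What the plan says.** Section 6.3 gives the allocation schedule under the note "Randomization ratios over the course of the study due to therapist availability". The schedule has three entries:

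- The first period, favouring MC, reads "November 2019-December 2020 = 2:1, MC:Control".
- The second, with the ratio reversed, reads "January 2021- ~2021 = 1:2, MC:Control".
- The third, with equal allocation and a start date marked as approximate, reads "July 2021- = 1:1, MC:Control".

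The stratification factors are sex and MoCA score; calendar period is not one of them. The amendment history (10.2) dates the schedule to version 4, December 2020, gives transparency as the reason, and lists no matching change to the analysis.

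For Aim 3, section 9.4 specifies a "mixed model repeated measures ANOVA (2: group X 3: time point") model, chosen in order to "use statistical contrasts to compare pre-post and pre-follow up changes across group". The information criteria mentioned there choose the within-subject correlation structure only. Section 8.1 says that some data will be collected as covariates, and section 6.5 allows exploratory adjustment for medication changes. Neither names enrolment period or allocation ratio. Section 9.2 says the purpose of measuring the treatment effect is to "obtain effect size estimates to power an efficacy trial".

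**The concern.** Randomization is valid within each period. Pooling periods that used different ratios, without conditioning on period, gives up part of that protection: early participants are over-represented in MC, and those enrolled in the 1:2 period are over-represented in Control.

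What matters is a period effect on **change**. One that is equal at all time points cancels from the pre-post and pre-follow-up contrasts.

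The documents report no period effect, but they do describe conditions that varied over the study. Section 7.1 mentions COVID-19 as a reason for long treatment pauses. Section 6.2.1 has tape review falling from 50% to 20%. Section 10.2 adds a telephone MoCA screen in December 2020, just as the ratio reversed. None of this proves an effect on change in Goal Attainment; it means that the absence of one is an assumption.

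At stake is the effect size carried into the definitive trial. The failure criterion for Aim 3 in section 3 is worded as average change and is not affected by this point.

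**Working it through.** **Inputs.** From section 9.2: N = 60, 30 per group, SD of change 0.97, two-sided alpha 0.05, 90% power, detectable difference 0.85. From section 6.3: the ratios. Assumed: enrolment per period, exact ratios within period, complete data.

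**The plan's own figure.** Detectable difference = (1.960 + 1.282) × 0.97 × √(2/30) = 0.812 (normal approximation), or 0.826 with the t distribution. A difference of 0.85 needs 28 per group (normal) or 29 (t). The stated 0.85 at 30 per group reproduces, slightly on the cautious side.

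**Bias.** With complete data the group-by-time contrast is the difference in mean change, so

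bias = Σ over periods of (share of MC arm in period − share of Control arm in period) × period effect on change.

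Example, 24/24/12: MC has 16, 8 and 6; Control has 8, 16 and 6. The 2:1-period weight is 16/30 − 8/30 = 0.267.

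**Standard errors.** Planned model: 0.97 × √(1/n_MC + 1/n_C). With period terms: 0.97 / √(Σ n_MC·n_C/(n_MC + n_C)), summed over periods.

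The first four splits assume constant accrual from November 2019, with 14 months at 2:1 and 6 months at 1:2. The rates are 4/month (H1), 3/month (preliminary study, section 9.4), 2.5/month (60 over 24 months) and 2/month. The others assume uneven accrual.

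| Split (2:1 / 1:2 / 1:1) | Bias per point of 2:1-period shift | SE planned | SE with period | Rise | Coverage of planned 95% CI at 0.5-point shift |
|---|---|---|---|---|---|
| 56/4/0 | 0.091 | 0.262 | 0.266 | 1.5% | 95.3% |
| 42/18/0 | 0.285 | 0.253 | 0.266 | 5.1% | 92.7% |
| 35/15/10 | 0.263 | 0.252 | 0.263 | 4.3% | 93.4% |
| 28/12/20 | 0.230 | 0.251 | 0.260 | 3.5% | 94.0% |
| 24/24/12 | 0.267 | 0.250 | 0.262 | 4.8% | 93.2% |
| 15/15/30 | 0.167 | 0.250 | 0.258 | 2.9% | 94.9% |
| 12/12/36 | 0.133 | 0.250 | 0.256 | 2.3% | 95.2% |
| 30/30/0 | 0.333 | 0.250 | 0.266 | 6.1% | 91.6% |

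A 0.25-point shift therefore gives 0.02 to 0.08 points of bias, and a 0.5-point shift gives 0.05 to 0.17. The 95% half-width is 0.50 to 0.52. A shift confined to the 1:1 period gives at most 0.06 per point in these splits, but that is not a general bound: 20/5/35 gives 0.098. Bias tends to zero if almost everyone enrols in one period.

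**Which term removes it.** Repeated-measures check by generalized least squares, three time points, 24/24/12, 0.5-point shift on change in the 2:1 period:

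| Model | Bias | SE |
|---|---|---|
| Group × time | 0.133 | 0.2505 |
| Plus period main effect | 0.133 | 0.2505 |
| Plus period and period × time | 0.000 | 0.2624 |

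Main effects of sex and MoCA stratum likewise leave the contrast and its SE unchanged.

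**Simulation.** 20,000 trials per scenario, 20 enrolled per period, no treatment effect. With a shift of 0.5 or 1.0 points from the second period onward, the unadjusted bias is −0.11 or −0.23 and type I error is 7.1% or 12.3%. With period adjustment, bias is within 0.003 of zero and type I error is 4.9%. With no period effect, both analyses reject about 5%.

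**Carried into the next trial.** Per-arm n = 2 × ((1.960 + 1.282) × 0.97 / d)².

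| d used for planning | n per arm |
|---|---|
| 0.85 (taken as true) | 28 |
| 0.895 to 1.02 (bias +0.05 to +0.17) | 25 to 20, true power 87% to 79% |
| 0.805 to 0.68 (opposite sign) | 31 to 43 |
| 0.35 to 1.35 (sampling error alone, ±0.50) | 162 to 11 |

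**The case against.** - **The harm is hypothetical.** No period effect is shown, and without one the planned contrast is unbiased. This stands: only the missing term is certain.
- **Adjusting may cost more than it saves.** For a 2:1-period shift below about 0.27 to 0.51 points, depending on the split, the unadjusted contrast has the smaller root mean squared error. At 24/24/12 and a 0.25-point shift it is 0.259 against 0.262. This is correct, but the margin is tiny, and it is no strong reason to keep an avoidable confounder whose size is unknown.
- **Aim 3 is exploratory, and uncertainty is acknowledged.** Section 9.4 plans confidence intervals and a sample size table over several effect sizes. Sampling error is clearly the larger problem. But those devices describe spread around the estimate; they do not correct a shifted centre.
- **The range leans on extreme splits.** Both ends, 0.09 and 0.33, leave the 1:1 period empty, and four of the eight splits do not give 30 per arm. Those with 30 per arm and a populated 1:1 period give 0.13 to 0.27. That is a fair narrowing and leaves the conclusion as it is.
- **Period terms miss therapist effects within one arm.** The ratios changed because of therapist availability. A 0.5-point shift in MC only, in the 2:1 period at 24/24/12, gives a bias of 0.267 unadjusted and 0.195 with period terms. This limit stands and should be stated.
- **The approximate dates were forecasts.** That is plausible, since the last listed amendment is May 2021. The actual dates are still needed to define period.

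**Conclusion.** The concern holds. Allocation is tied to enrolment period by design, and nothing in the documents brings period into the Aim 3 contrast. Whether this produces bias, and in which direction, depends on a period effect that the documents neither show nor exclude. If there is one, between 9% and 33% of a 2:1-period shift reaches the contrast under the assumed splits. That is modest beside a half-width of about 0.5 points, but it is systematic.

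The figures rest on SD 0.97, 60 participants with complete data, exact ratios within period and assumed enrolment per period. The point should be fixed because the remedy is cheap and protects the effect size that Aim 3 is meant to deliver. It does not threaten the feasibility or fidelity aims.

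**What to change.** In section 9.4, add randomization period and period × time point to the Aim 3 mixed model, and take the pre-post and pre-follow-up contrasts from it. Define period as the allocation ratio in force when the participant was randomized, taken from the REDCap record. Report the group × time model as a sensitivity analysis. If sex and MoCA stratum are added, include their interactions with time point too.

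In section 6.3, replace the approximate dates with the actual date of each ratio change, and report enrolment by period and arm. State that the period terms remove only effects common to both arms, not therapist changes within one arm.

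The cost is a few lines of analysis text, the dates and one table. The terms use 2 degrees of freedom per change contrast (six fixed-effect parameters across three time points). The detectable difference at 90% power (normal approximation) moves from 0.81-0.85 to 0.83-0.86, still close to the planned 0.85.

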6.4 STUDY INTERVENTION/EXPERIMENTAL MANIPULATION ADHERENCE

Participant engagement in and adherence to the intervention are primary outcomes of this study (Aim 2b) and thus will be formally assessed.

See section 8.1

6.5 CONCOMITANT THERAPY

There are no medication exclusions for this protocol. Medication information will be obtained from electronic medical records and confirmed with the participant at the Pre-treatment assessment. Medical records will be reviewed after participation to determine whether there were any changes over the course of the study. If so, they will be documented and potentially accounted for in analyses (exploratory).

7 STUDY INTERVENTION/EXPERIMENTAL MANIPULATION DISCONTINUATION AND PARTICIPANT DISCONTINUATION/WITHDRAWAL

7.1 DISCONTINUATION OF STUDY INTERVENTION/EXPERIMENTAL MANIPULATION

Participants may discontinue the study intervention before receiving 10 treatment sessions for a variety of reasons (e.g., adverse events, no longer interested, other obligations taking precedence). Temporary discontinuation of the study intervention can also be considered; however, this should not last longer than 3 weeks unless absolutely necessary (i.e., the COVID-19 situation). When a participant permanently discontinues from the study intervention but not from the study, remaining study procedures will be completed as indicated by the study protocol (i.e, Post-treatment assessment within 2 weeks after last treatment session, and Follow-up assessment 3 months after that). The reason(s) for discontinuing the participant from the intervention will be documented on the Participant Tracking sheet.

7.2 PARTICIPANT DISCONTINUATION/WITHDRAWAL FROM THE STUDY

Participants may withdraw voluntarily from the study or the study intervention at any time, but investigators will seek to minimize participant discontinuation/withdrawal from the study except for safety reasons. An investigator may discontinue a participant from the study for the following reasons:

- Lost-to-follow up; unable to contact subject (see **Section 7.3, Lost to Follow-Up**)
- Any event or medical condition or situation occurs such that continued collection of study data would not be in the best interest of the participant or might require an additional treatment that would confound the interpretation of the study.
- The participant meets an exclusion criterion (either newly developed or not previously recognized) that precludes further study participation.

The reason for participant discontinuation or withdrawal from the study will be documented on the Master File. Because an aim of this study is to track retention and determine attrition rates to power a future full-scale trial, participants who discontinue/withdraw from the study will not be replaced.

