To obtain preliminary estimates of effect on self-efficacy.	Cognitive Self-efficacy Scale, General Self-efficacy Scale	
Tertiary/Exploratory		
To obtain preliminary estimates of effect on participation.	NeuroQOL Ability to Participate in Social Roles and Activities	

The following criteria will be used to declare failure:

Aim 1: Feasibility

- ≤ 60% retention in the study intervention

- $\leq 75\%$ retention in the study (80-85% is typically considered good in behavioral trials; e.g., Abshire et al., 2017; Coday et al., 2005)
- Note: Participants excluded post-Randomization count as failures in the above retention endpoints.

Aim 2: Fidelity

- Therapist adherence to protocol: Average $\leq 75\%$
- Therapist competence in administration: Average < 2
- Participant satisfaction: Average Client Satisfaction Questionnaire score ≤ 16
- Participant engagement: Average Rehabilitation Participation Scale score ≤ 3

Aim 3: Effect

- Average Bangor Goal Setting Interview Goal Attainment change of ≤ 1 with lower 95% CB below 0.

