9.3 POPULATIONS FOR ANALYSES

Our primary population for analysis of treatment effect (Aim 3) will be the Intention-to-Treat (ITT) Analysis Population (i.e., all randomized participants). We will also conduct Per-Protocol analyses on the subset considered to have completed the intervention (at least 4 treatment sessions).

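### Section 7.2 lets investigators end data collection on randomised participants for a confounding treatment or an exclusion criterion, creating avoidable and possibly outcome-related missing data in the Aim 3 ITT analysis

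*Combined protocol and SAP*

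**What the plan says.** Section 7.2 opens its list with "An investigator may discontinue a participant from the study for the following reasons". The discontinuation is from the study, not only from treatment. Two of the listed grounds matter here:

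- A situation that "might require an additional treatment that would confound the interpretation of the study". This is the second half of a bullet whose first half covers the participant's best interest.
- "The participant meets an exclusion criterion (either newly developed or not previously recognized) that precludes further study participation".

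Section 7.1 deals with the other kind of stopping: "When a participant permanently discontinues from the study intervention but not from the study, remaining study procedures will be completed". No equivalent provision covers people discontinued under Section 7.2.

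Section 9.3 says that the primary population for the Aim 3 treatment effect "will be the Intention-to-Treat (ITT) Analysis Population (i.e., all randomized participants"). Section 9.4 gives the model: "We will compare treatment effects (Goal Attainment) using mixed model repeated measures ANOVA (2: group X 3: time point"). It states no missing-data assumption and no sensitivity analysis for missing outcomes.

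Section 3 deals with such people for retention only: "Participants excluded post-Randomization count as failures in the above retention endpoints". Nothing comparable is said for goal attainment.

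**The concern.** Both grounds operate after randomisation. Under Section 5.2 the exclusion criteria include dementia, a MoCA score below 21 and significant current psychiatric disorder. A participant who newly meets one of these may well be doing worse on functional cognition, which is what Aim 3 measures. The need for an additional treatment can likewise reflect a poor course. Ending data collection at that point may remove people because of how they are doing, and their later ratings are then missing by the investigator's decision and not by the participant's choice.

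Aim 3 exists to supply effect sizes for planning a definitive trial. A distortion in the pilot estimate would carry into that sample size. The loss is avoidable, since the participant may be willing and able to complete the remaining questionnaires.

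**Working it through.** **1. Does Section 7.2 end outcome collection?** Section 7.1 keeps Post and Follow-up for those who leave the intervention but not the study. Section 7.2 concerns leaving the study, and its best-interest wording is itself about continuing to collect data. Read together, a Section 7.2 withdrawal has no further assessment specified.

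**2. What data remain?** By the Schedule of Activities (Section 1.3) and Section 8.1, Goal Attainment is rated at treatment session 2, at Post and at Follow-up. Someone withdrawn during treatment contributes at most the session 2 rating, and someone withdrawn before session 2 contributes none. A likelihood-based mixed model is valid if data are missing at random, but here it has at most a baseline value to work from.

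**3. The plan's own figure.** Section 9.2 gives SD of change 0.97, 30 per group, two-sided 5% and 90% power, with a detectable difference of 0.85.

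- Normal approximation: 0.97 × (1.960 + 1.282) × √(2/30) = 0.81.
- Two-sample t calculation: 0.83. Power for 0.85 is 91.6%.

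The stated figure is reproduced, slightly on the cautious side.

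**4. Sampling error for scale.** The 95% half-width for the difference in mean change is 2.00 × 0.97 × √(2/30) = 0.50.

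**5. Possible shift.** Let K be the mean change of those kept in an arm, m the share withdrawn on these grounds, and D the shortfall in mean change of those withdrawn. The mean for all randomised in that arm is (1 − m)K + m(K − D) = K − mD, so observed data overstate it by mD. With the same D in both arms, the MC minus Control difference shifts by

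(m1 − m0) × D,

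where m1 is the share in MC and m0 the share in Control. The documents give none of m1, m0 or D. The values below are assumptions, with D set to one SD of change (0.97):

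| m1 vs m0 | Shift (points) |
|---|---|
| 5% vs 0% | 0.05 × 0.97 = 0.05 |
| 10% vs 0% | 0.10 × 0.97 = 0.10 |
| 15% vs 5% | 0.10 × 0.97 = 0.10 |
| 15% vs 0% | 0.15 × 0.97 = 0.15 |
| 15% vs 15% | 0 |

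The sign reverses if Control loses more. A harsher assumption, D = 2.4 (the preliminary mean change in Section 9.2, so that those withdrawn would not have improved at all), gives 0.12 at 5% vs 0% and 0.36 at 15% vs 0%. Both are still below the half-width of 0.50.

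The 15% rows are an upper end: 15% is the plan's whole attrition allowance in Section 9.2, and total loss in the preliminary study was 12.5% (87.5% retention, Section 9.4).

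**The case against.** Much can be said for the plan as written. Withdrawal is discretionary, Section 7.2 says investigators will seek to minimise it, reasons are documented, and participants are not replaced. Section 7.1 already separates stopping treatment from leaving the study in the ordinary case. Section 6.3 blinds the principal investigator, the coordinator and the testers, which limits withdrawal driven by arm. Aim 3 is exploratory, and Section 9.4 plans a sample-size table because pilot estimates are uncertain. For Aim 1, post-randomisation exclusions count as failures, which is conservative. All of this stands and limits the weight of the point. It does not remove it: therapists know the arm, Section 7.3 gives the OT or the coordinator a part in judging whether a participant should continue after a missed visit, and blinded withdrawal can still follow outcome.

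Four stronger readings are tempting and are not supported:

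- **That a participant who does poorly and seeks other cognitive therapy will be removed.** Section 7.2 permits removal and does not require it. Section 5.3 asks participants to refrain from such therapy but attaches no removal, and Section 6.5 records medication changes without making them a ground for withdrawal.
- **That the mixed model certainly fails.** It is valid under missing at random. That assumption is unstated and doubtful here, but the documents do not show it to be false.
- **That every exclusion under Section 7.2 is outcome-driven.** A criterion not recognised at entry is an eligibility error fixed at baseline. The Section 3 note does not show that outcome-related exclusions are expected.
- **That the overstatement of one arm's mean can be expressed as a percentage of 0.85.** That figure is a between-arm difference, so the comparison works only if the other arm loses nobody on these grounds.

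Nor is the ITT definition itself contradicted. Withdrawn participants remain in the randomised set; what is missing is their outcomes.

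**Conclusion.** The point holds in a limited form. Section 7.2 permits investigator-made loss of Post and Follow-up data on two grounds that sit badly with an analysis of all randomised participants. The added-treatment ground and newly developed exclusion criteria can be related to outcome; previously unrecognised criteria are less likely to be, but they still remove data that the ITT analysis needs.

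With D = 0.97, the shift in the between-arm difference runs from zero (equal and similar losses) through 0.05 (5% vs 0%) to 0.15 (15% vs 0%), against a half-width of about 0.50. This is modest beside sampling error. It rests on assumed shares, an assumed shortfall common to both arms, and an analysis that recovers nothing from the baseline rating. The case for change is that the loss is avoidable and cheap to prevent, not that a large bias has been shown.

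**What to change.** In Section 7.2, delete two grounds for ending data collection: the possible need for a confounding treatment, and meeting an exclusion criterion. State that such participants stay in scheduled Post and Follow-up assessment and in the ITT set unless they withdraw consent, cannot be reached, or continued data collection is not in their best interest. Record the added treatment or the criterion, with its date, and use it only in per-protocol or sensitivity analyses. In Section 9.4, state the missing-data assumption behind the mixed model and add a sensitivity analysis for departures from it.

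This extends what Section 7.1 already does. Decisions about care and about stopping the intervention are unaffected.

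The cost is protocol wording plus a few more questionnaires and assessments. Goal Attainment at Post and Follow-up is already collected by web or mail (Section 1.3). The ITT estimate will include some people who had other treatment, which is inherent in analysing all randomised participants.
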